4.2.8 Pharmacokinetic and immunogenicity variables

PK and immunogenicity data will be collected during the double blinded period and the OLE period according to the SoA Table 2 and Table 3, respectively, in the CSP. PK and immunogenicity data from the DB period will be descriptively summarised at the primary DBL, while additional data from the OLE period will be reported at the final DBL.

4.2.8.1 Analysis of pharmacokinetic variables

Benralizumab serum concentrations will be summarised by using descriptive statistics during the DB period using the PK analysis set, and during the OLE period using the OLE analysis set. In addition, geometric mean, coefficient of variation (CV), lower (Q1), and upper (Q3) quartiles will also be reported.

Serum concentrations, that are below the LLOQ (<LLOQ) or if there are missing values, will be handled as follows:

- All values <LLOQ will be set to LLOQ/2. Missing values will be set to “NA”.
- At a time point where mean is <LLOQ, Not Applicable (N/A) will be written in the field for SD, CV%, and 95% CI. The maximum value will be reported from individual data. If median is <LLOQ then shall be reported as <LLOQ, otherwise reported from individual data. The minimum value will be reported as <LLOQ.
- If all values are <LLOQ at a time point, no descriptive statistics will be calculated for that time point. Not Applicable (N/A) will be written in the field for SD, CV%, and 95% CI, and <LLOQ will be written in fields for the mean, geometric mean, minimum, median and maximum.

The LLOQ of Benralizumab in serum will be 3.86 ng/mL.

4.2.8.2 Analysis of immunogenicity variables

Anti-drug antibody assessment will be conducted and analysed as per the details in Appendix 8.7.

4.2.9 Exploratory efficacy variables

All exploratory efficacy endpoints will be collected during the double blinded period according to the SoA Table 2 in the CSP, except asthma exacerbation will be further collected during the OLE period (CSP Table 3). Therefore following analyses specified in Section 4.2.9.1 to Section 4.2.9.5 only apply to the double blind period at the primary DBL. Asthma exacerbation during the OLE period will descriptively summarized at final DBL.

4.2.9.1 Asthma control questionnaire 6

The observed mean ACQ-6 and the changes from baseline will be summarised by treatment group and by visit using descriptive statistics for all patients in PFAS in DB period.

The changes from baseline in mean ACQ-6 will be analysed under the treatment policy estimand where all data observed through Week 56 is included regardless of treatment discontinuation, surgery or SCS use for CRSwNP. The analysis will be conducted using ANCOVA for repeated measures (assuming missing at random) with treatment arm, baseline ACQ-6 scores, visit, region, CCI [REDACTED] and treatment×visit as covariates. See Appendix 8.5 for more details.

The ACQ-6 responder at Week 24 and at Week 56 will be analysed using the logistic regression with treatment arm, baseline ACQ-6, region, CCI [REDACTED] as covariates.

Observed data will be used; subjects with missing or non-evaluable observations at the timepoint of interest are counted as non-responders.

The number and proportion of responders and the number and proportion of patients by asthma control status will be summarised by treatment group for all patients in PFAS.

4.2.9.2 Asthma exacerbation rate

The number of exacerbations associated with SCS use, hospitalisation, ER visit, and urgent care visit will be summarised by treatment group during DB period for all patients in PFAS, and during OLE period for patients included in OLE analysis, respectively.

The annual exacerbation rate (as defined in Section 3.7.2) during the DB period will be analysed using a negative binomial model. The response variable in the model will be the number of asthma exacerbations experienced by a patient during the DB period. The model will include covariates of treatment group, region, CCI [REDACTED] and number of prior exacerbations as covariates. The logarithm of the patient's corresponding follow-up time during the DB period will be used as an offset variable in the model to adjust for patients having different exposure times during which exacerbations could occur. Marginal standardisation methods will be used on the model estimates for all negative binomial analyses, unless otherwise specified.

4.2.9.3 PGI-S and PGI-C

PGI-C response categories are described in in Section 3.7.3. The number and percentage of patients in each category of PGI-S and PGI-C responses, as well as PGI-C improvement categories will be summarised by treatment group and by time point during the DB period using the PFAS. Non-rescued subjects whose post-baseline observations are all missing are excluded from this analysis. Data after surgery for CRSwNP are imputed by WP and data after SCS use for CRSwNP are imputed by WOCF.

4.2.9.4 Healthcare resource utilisation

The following unplanned/unscheduled healthcare resource use (HRU) due to (a) nasal polyps, (b) asthma exacerbation (c) other reasons will be collected during the DB period.

- General and intensive care hospitalisations and lengths of stay
- Emergency room visits
- Urgent care visits

The frequency, crude rate (as defined in Section 3.7.4), and annualised rate (defined as *crude rate* * 365.25) of the HRU listed above and the total number of day hospitalised during the DB period will be summarised by reasons and treatment group using descriptive statistics for all patients in the PFAS.

4.2.9.5 Biomarkers

Biomarker values including blood eosinophils **CCI** as well as changes from baseline will be summarised by standard summary statistics for all patients in the FAS. Blood eosinophils will be presented for the DB period at the primary DBL and for the OLE period at the final DBL. **CCI** is collected during the DB period only so will be reported at the primary DBL.

Subgroup analyses by quartiles of blood eosinophils will be conducted as mentioned in Section 4.2.5.3 in order to assess the impact of blood eosinophils on efficacy endpoints. In addition, the associations between the efficacy endpoints and baseline blood eosinophil counts **CCI** will be evaluated by Loess plots against primary endpoint variables NPS and NBS for all patients in the PFAS.

The analyses of other exploratory biomarkers may be conducted and reported outside the CSR.

4.2.10 Safety outcome variables

All safety variables will be summarised by treatment group using descriptive statistics as appropriate. Adverse events (AEs) will be summarised during DB period using safety analysis set, as well as during OLE period (as defined in Section 3.1.1) using the OLE analysis set. All available safety data during the DB period and selected AE endpoints during the OLE period will be reported at the primary DBL. Remaining safety data on AE, laboratory, vital sign from the OLE period will be summarised and reported at the final DBL.

4.2.10.1 Adverse events

Summary of adverse events over the DB period

AEs will be summarised over the DB period by treatment group for all patients in the safety analysis set. An overview of AEs will present for each treatment group the number and percentage of patients with any AE, serious AEs (SAEs), SAEs with outcome of death, and AEs leading to discontinuation of IP (DAEs).

Adverse events, AEs with outcome of death, SAEs, DAEs, and possibly related AE (assessed by investigators) will be summarised by SOC and PT assigned to the event by MedDRA. For each PT, the number and percentage of patients reporting at least one occurrence will be presented, i.e., for a patient multiple occurrences of an AE will only be counted once.

Additional summaries of all AEs and common AE (PT Frequency of $\geq 3\%$ in any treatment arm) will be presented by PT. AEs will also be summarised by PT and maximum intensity. If a patient reports multiple occurrences of the same AE within the same analysis period, the maximum intensity will be taken as the highest recorded maximum intensity (the order being mild, moderate, and severe). Adverse events of injection site reactions (MedDRA High Level Term of injection site reactions), hypersensitivity (standardised MedDRA query (SMQ) [Narrow] of hypersensitivity), malignancy (SMQ of malignant tumours) and helminth

infections (MedDRA High Level Group Term of helminthic disorders) will be summarised by preferred term.

The crude rate and exposure adjusted incidence rate (EAIR) (PHUSE 2017) will be reported for any AE, common AE, SAE, AEs leading to IP discontinuation, adverse event of interest. Both crude rate and EAIR will be expressed in terms of events per 100 patient-years. Crude rate per 100 patient-years is defined as number of subjects with AEs divided by total patient years across all subjects in a given treatment group, multiplied by 100. EAIR per 100 patient-years is calculated based on each AE term, defined as number of subjects with an AE divided by the total number of days at risk for that AEs across all subjects in given group, multiplied by 365.25 multiplied by 100. Total number of days at risk for an AE is defined as the duration from the first dose of IP to the start date of the first AE for the subjects with that AE, or the duration from the first dose of IP to end of double-blind period for subject without that AE. In case AE onset date is completely missing, time at-risk will be imputed as 1 day assuming the AE starts on the same date of the first dose of study treatment.

EAIR comparisons between treatment groups (i.e. risk difference in exposure-adjusted incidence rates) and 95% CI based on Miettinen and Nurminen (M-N) method (Liu et al. 2006, Miettinen and Nurminen 1985) will be reported. The risk difference scale is chosen to directly reflect the difference in magnitude of patients that could be affected by a risk.

For common AEs and AEs of interest (injection site reactions, hypersensitivity, malignancy and helminth infections), comparisons between treatment arms will be presented graphically in a panel plot with the left panel showing a dot plot of the proportion of patients reporting each AE by treatment arm, and the right panel showing a corresponding forest plot of estimated risk differences with M-N associated 2-sided 95% CIs.

Key patient listings for AEs with outcome of death, SAEs, or DAEs will be presented.

Summary of adverse events over the OLE period

The analysis of AEs during the DB period as described above will be repeated for the OLE period in the OLE analysis set. AE overview and summaries by SOC and PT for AE, AEs with outcome of death, SAEs and DAEs over the OLE period will be reported at the primary DBL, while remaining AE summaries for OLE period will be reported at the final DBL.

4.2.10.2 Laboratory data

All protocol-specified continuous laboratory parameters will be summarised descriptively for absolute value at each time point by treatment group, together with the corresponding changes from baseline. This will be provided for the DB period at primary DBL as well as for the OLE period at final DBL. All parameters will be summarised in SI units unless otherwise specified.

Central laboratory reference ranges will be used for the identification of abnormalities, and a shift table will be produced for each laboratory parameter to display low, normal, and high

values. The shift tables will present baseline and maximum/minimum post-baseline value, as applicable for each parameter and will include patients with both baseline and post-baseline data. Shift tables will use all available data during DB period and during OLE period, respectively.

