- e. Visit 11 is the last double-blind visit and the first OLE visit. Only patients who enter OLE will receive IP (first dose of open-label Benralizumab) at this visit. All assessments at Visit 11 to be performed before administration of open-label benralizumab.
- f. Patients to complete available assessments in-clinic prior to other study procedures.

- g. UPSIT smell test will be performed in all countries which have validated version of the test.
- h. Assessed at EoDB. For IPD patients only do assessment if at least 16 weeks since the previous CT scan. In case of surgery during the double-blind part of the study, the CT scan should be done prior to surgery instead of at week 56.
- i. Results will only be used as baseline data. Will not be used for eligibility check.
- j. At dosing visits, must be collected pre-dose.
- k. Additional exploratory biomarker samples (excluding CCI and DNA sample (optional) will be collected in all participating countries except for China Mainland. DNA sample will not be collected in China Taiwan.
- l. Assessed at EoDB. For IPD patients only do assessment if the time period between randomization and IPD visit is ≥ 24 weeks.
- m. CCI is the only exploratory biomarker collected in China Mainland.
- n. Samples can be collected at any time from Week 0 (V3) after genetic consent is signed.
- o. All V3 procedures and assessments must be performed prior to randomization/IP dosing.
- p. IP administration should be the last activity of the visit. All visit procedures should be done prior to dosing.
- q. IP administration will be applied to patients who enter the OLE.

ACQ-6- Asthma Control Questionnaire-6; CRSwNP- Chronic rhinosinusitis with nasal polyps; CT- Computed tomography; CCI ; EoDB- End of double-blind; HRU- Healthcare resource utilization; CCI IPD- Investigational product discontinuation; PGI-C- Patient Global Impression of Change; PGI-S- Patient Global Impression of Severity; PK- Pharmacokinetics; PRO- Patient -reported outcome; SCS- Systemic corticosteroids; SF-36v2- Short Form 36-item Health Survey, Version 2; SNOT-22- SinoNasal Outcome Test, 22 item; UNS- Unscheduled; UPSIT- University of Pennsylvania Smell Identification Test.

Table 3 Schedule of Activities – For the Open-label Extension and Follow-up

Study period	Open-label treatment period								FU/IPD ^{e)}	UNS ^{d)}	Refer to section
	V12	V13 ^{b)}	V14 ^{b)}	V15	V16 ^{b)}	V17 ^{b)}	V18 ^{b)}	V19			
Visit	W60	W64	W72	W80	W88	W96	W104	W112			
Week											

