8.2.1. Clinical safety laboratory assessments

See [Table 13](#) for the list of clinical safety laboratory tests to be performed and to the SoA for the timing and frequency. All protocol-required laboratory assessments, as defined in the table, must be conducted in accordance with the laboratory manual and the SoA. Clinical chemistry assessments should be collected under fasting conditions (fasting starts at least 8 hours before sample collection).

For information on methods of collection, assessment, labelling, storage, and shipment of samples, please refer to the separate Laboratory Manual.

The Investigator should make an assessment of the available results with regard to clinically relevant abnormalities. The laboratory results should be signed and dated and retained at centre as source data for laboratory variables.

For information on how AEs based on laboratory tests should be recorded and reported, see [Section 8.3.7](#).

Table 13 Laboratory safety variables

Haematology/Haemostasis (whole blood)	Clinical Chemistry (serum or plasma)
B-Haemoglobin (Hb)	S/P-Alkaline phosphatase (ALP)
B-Leukocyte count	S/P-Aspartate aminotransferase (AST)
B-Mean corpuscular volume (MCV)	S/P-Alanine aminotransferase (ALT)
B-Red blood cell (RBC)	S/P-Bilirubin, total
B-Platelet count	S/P-Blood urea nitrogen (BUN)
B-Leukocyte differential count and percentage	S/P-Calcium, total
	S/P-Creatinine
	S/P-Gamma-GT (gamma-glutamyl transpeptidase)

Haematology/Haemostasis (whole blood)	Clinical Chemistry (serum or plasma)
	S/P-Glucose
	S/P-Potassium
	S/P-Sodium

^a Eosinophils, basophils and monocytes counts and percentage after V3 will be redacted from central laboratory reports

Samples for the analysis of the peripheral blood eosinophils will be performed in the central laboratory as part of the routine haematology assessment (CBC).

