9.4.2.2. Analyses of safety variables

Safety data will be presented using descriptive statistics unless otherwise specified. In general, the baseline value for statistical analysis is the last non-missing value prior to administration of the first dose of IP. Details will be described in the SAP.

Adverse Events

Adverse events will be coded using the most recent version of the Medical Dictionary for Regulatory Activities (MedDRA) that will have been released for execution at AZ/designee. AEs will be presented for each treatment group by SOC and/or PT covering number and percentage of patients reporting at least one event and number of events where appropriate.

An overview of AEs will present for each treatment group the number and percentage of patients with any AE, AEs with outcome of death, serious AEs, and AEs leading to discontinuation of IP. Separate AE tables will be provided taken into consideration

relationship as assessed by the investigator, intensity, seriousness, death and events leading to discontinuation of IP. An additional table will present number and percentage of patients with most common AEs (frequency of $\geq 3\%$). Key patient information will be presented for patients with AEs with outcome of death, serious AEs, and AEs leading to discontinuation of IP. An AE listing for the safety analysis set will cover details for each individual AE. Full details of AE analyses will be provided in the SAP.

The following events are considered treatment emergent:

- Adverse events with an onset date on or after first dose of IP
- Worsening of pre-existing events on or after first dose of IP

Vital signs

Vital sign parameters will be presented for each treatment group. Summary statistics for continuous variables cover n, Min, median, and Max. For each scheduled post-baseline visit, descriptive statistics for all vital sign parameters will be presented for observed values and change from baseline. Details of vital sign analyses will be provided in the SAP.

Clinical Laboratory Measurements

Laboratory data will be summarized per treatment group by presenting shift tables using normal ranges (baseline to most extreme post-baseline value) and by presenting summary statistics of observed and change from baseline values. Details of laboratory data analyses will be provided in the SAP.

ECG

Summary statistics for the overall evaluation of ECG will be tabulated per treatment group. Details of ECG analyses will be provided in the SAP.

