Other	21SEP2021	Some small text updates throughout the document, correcting typos or adding clarity in the analysis	N/A	To add clarity on the reporting of the data
Data presentation	21SEP2021	Updated ADA analysis in Appendix 8.7	N/A	To add clarity on the analysis and reporting of the ADA data in OLE period and on-study
Statistical analysis method for the primary or secondary endpoints	21SEP2021	Added additional supplementary analysis for LMS in Section 4.2.6.2	N/A	To add clarity on the reporting of the data
Other	21SEP2021	Added clarity that analysis for China/Japan submission will not be reported in CSR in Section 4.1.1	N/A	To add clarity on the reporting of the data
Statistical analysis method for the primary or secondary endpoints	21SEP2021	Added additional responder analysis for NBS in Section 4.2.5.4 and additional supplemental analysis for LMS in Section 4.2.6.2	N/A	To be consist with the global NP program
Data presentation	21SEP2021	Removed the analysis of Hy's law from Section 4.2.10.2	Yes (CSP version 4.0, 16MAR2021)	Data no longer collected
Other	12MAY2021	Updated Section 1 by adding OLE treatment period and other updates for the changes in the study design and number of patients	Yes (CSP version 4.0, 16MAR2021)	To be aligned with the CSP amendment v4.0
Other	12MAY2021	Added OLE analysis set in Section 2.1	Yes (CSP version 4.0, 16MAR2021)	To be aligned with the CSP amendment v4.0

Data representation	12MAY2021	Updated the corresponding subsections of 3.1 to address the OLE period	Yes (CSP version 4.0, 16MAR2021)	To be aligned with the CSP amendment v4.0
Primary or Secondary Endpoints	12MAY2021	Added key secondary endpoints: DSS and SNOT-22)	Yes (CSP version 4.0, 16MAR2021)	To be aligned with the CSP amendment v4.0
Statistical analysis method for the primary or secondary endpoints	12MAY2021	Analysis of continuous endpoints changed from MMRM to ANCOVA with MI. Imputation approach for intercurrent events changed from censoring (for treatment discontinuation, surgery for CRSwNP, or SCS use for CRSwNP) to composite Worst Possible after rescue by surgery for CRSwNP. WOCF after SCS use for CRSwNP is retained Changed the covariates in the ANCOVA model as well to region CCI Added Week 40 to responder analyses and subgroup analyses	Yes (CSP version 4.0, 16MAR2021)	To be aligned with the CSP amendment v4.0 Week 40 is added to be consistent with the global NP program.

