3.1.3 The definition of baseline

In general, the last valid value on or prior to the date of randomisation will serve as the baseline measurement for efficacy endpoints while the last valid value prior to first dose of study treatment will serve as the baseline measurement for safety endpoints. If there is no value prior to randomisation (or the first dose of study treatment, depending on the endpoint), then the baseline value will not be imputed and will be set to missing. No safety data known to be collected post first dose will be used in determining the baseline value, unless otherwise specified.

For the NPSD (which includes the NBS and DSS), the baseline is the mean of daily responses collected from Day -13 to Day 1. The mean is calculated as the sum of all non-missing daily scores if at least 8 days (>50%) over these 14 sequential days have available data, divided by the number of non-missing daily scores. Otherwise, the baseline is set to missing.

Baseline value for the OLE will be set to the last recorded value prior to starting the first dose of benralizumab in the OLE.

Summaries of demographics, safety, immunogenicity, etc. will be provided for the DB period and may be repeated for the OLE period using the OLE baseline values among all patients in the OLE analysis set including patients who were previously on benralizumab.

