3.8.2 Laboratory variables

Laboratory assessment values and normal ranges will be presented in the International System (SI) unit. Eosinophil data will be presented in both SI and conventional units (cells/ μ L) in summaries.

Changes in haematology and clinical chemistry variables between baseline and each post-baseline assessment will be calculated. There will be no imputation for missing values. For values recorded with a leading greater than or less than ('>', '<') symbol, the reported numeric value will be used for analysis and the value with the symbol will be included in the listings, unless otherwise specified. For example, a value of <0.01 will be analysed as 0.01 and listed as <0.01.

Absolute values will be compared to the relevant reference range and classified as low (below range), normal (within range or on limits) or high (above range). All absolute values falling outside the reference ranges will be flagged. The maximum or minimum value post-baseline will be calculated over the entire DB period and OLE period, respectively, for all patients.

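### Planned liver-test summaries (SAP 4.2.10.2) are ungraded and one test at a time, so counts per arm of graded ALT/AST or joint ALT/AST–bilirubin elevation are not generally recoverable

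*SAP*

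**What the plan says.** Protocol 9.4.2.2 commits to summary statistics of observed values and changes, and to "shift tables using normal ranges (baseline to most extreme post-baseline value"), and leaves the details to the SAP.

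SAP 4.2.10.2 supplies those two outputs: descriptive statistics by time point and arm, in SI units, and for the categories "a shift table will be produced for each laboratory parameter to display low, normal, and high" values. The shift runs from baseline to the maximum or minimum post-baseline value and uses all data in the period. SAP 3.8.2 gives the class rule: each value is "classified as low (below range), normal (within range or on limits) or high (above range"). Out-of-range values are flagged.

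The tests needed for a finer summary are in the chemistry panel (Protocol 8.2.1, Table 13): ALT, AST, ALP and "S/P-Bilirubin, total".

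On baseline, SAP 3.1.3 says that "the last valid value prior to first dose of study treatment will serve as the baseline measurement for safety endpoints". For chemistry this is normally the Visit 3 sample, of which Protocol Table 2, footnote i, says: "Results will only be used as baseline data. Will not be used for eligibility check".

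On adverse events, SAP 4.2.10.1 gives extra displays to common AEs and to "AEs of interest (injection site reactions, hypersensitivity, malignancy and helminth infections"). There is no hepatic group.

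**The concern.** The shift table has one open-ended class above the ULN. A marked, symptom-free ALT rise is counted with trivial ones, and a patient already above the ULN at baseline appears as high to high however far the value climbs. Such patients can be in the trial. Exclusion criterion 24 removes only confirmed ALT or AST of 3×ULN or more, criterion 12 accepts stable chronic liver disease, and the Visit 3 chemistry plays no part in eligibility.

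Because each test has its own table, nothing planned counts patients with both a transaminase and bilirubin raised.

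The AE tables are not built to fill the gap. Under Protocol 8.3.7, worsening in a protocol-mandated test becomes an AE only if it is serious or causes IP discontinuation. Where there are symptoms, the symptom is what gets reported.

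At stake is whether the study report can state, by arm, how many patients had a graded or joint elevation without choosing cut-offs after unblinding. Laboratory variables belong to the safety objective of the double-blind period and to the primary objective of the OLE.

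**Working it through.** The documents state no figure on this point, so there is none to reproduce. The check is whether the planned tables determine the counts. All patient values below are assumed for illustration; the documents give no liver-test data.

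**Inputs.** Planned arm size: 250 randomised 1:1, so 250/2 = 125 (Protocol 9.2). Class rule: high means above range (SAP 3.8.2). Continuous summaries: n, mean, SD, median, minimum, maximum (SAP 4.1).

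**1. Class rule.** 1.1×ULN and 12×ULN are both high. Baseline 1.5×ULN to a post-baseline 12×ULN is high to high, so the shift table shows no movement.

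**2. Joint count from separate margins.** With *a* patients high on one test and *b* on the other among *n*, the number high on both lies between max(0, a + b − n) and min(a, b).

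| a (ALT high) | b (bilirubin high) | n | Lower | Upper |
|---|---|---|---|---|
| 5 | 3 | 125 | max(0, −117) = 0 | 3 |
| 10 | 5 | 125 | max(0, −110) = 0 | 5 |

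The count is fixed when min(a, b) = 0: it is then exactly zero among patients in those tables. With ALT or AST as the criterion, this needs nobody high for bilirubin, or nobody high for either transaminase.

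**3. Graded count from the high count and the maximum.** Take two sets of five ALT-high patients, in multiples of ULN.

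| Set | Peak values | High | Maximum | ≥3× | ≥5× |
|---|---|---|---|---|---|
| 1 | 1.2, 1.3, 1.4, 1.5, 8.0 | 5 | 8.0 | 1 | 1 |
| 2 | 3.1, 3.2, 4.0, 5.5, 8.0 | 5 | 8.0 | 5 | 2 |

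The high count and the maximum agree, but the graded counts do not. The means would differ: the sums are 13.4 and 23.8, so with the other 120 patients identical the arm mean moves by (23.8 − 13.4)/125 = 0.08×ULN. A reader cannot turn that into a number of patients.

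**4. By-visit maxima and maximum changes.** These can show that at least one patient, or none, passed a level at a windowed visit. They give no count and do not link two tests within a patient. Under SAP 3.1.2 each window keeps the value closest to the scheduled day, so an unscheduled peak may drop out.

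**5. What the extra count would allow.** Exact 95% limits at n = 125:
- 0 patients: upper limit 1 − 0.025^(1/125) = 2.9%.
- 1 patient: 1/125 = 0.8%, limits 0.02% to 4.4%.

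The planned tables can supply the first numerator only in the zero-margin case of step 2, or where by-visit maxima rule out the level and no unscheduled peak was dropped. They do not in general supply the second.

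**The case against.** The SAP delivers exactly what the protocol promises, so there is no contradiction. Serious events and events leading to discontinuation are tabulated by arm, investigators must assess results for clinical relevance, all values are listed and out-of-range values are flagged. With about 250 patients and post-baseline chemistry scheduled only at Weeks 24 and 56 in the double-blind period, joint cases could be found by reading listings. A 1.5× to 12×ULN rise at a scheduled visit would also show in the maximum value and maximum change. Active liver disease and confirmed ALT/AST of 3×ULN or more are excluded. Of the cut-offs proposed, only 3×ULN appears in the documents, and there it is an eligibility limit.

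All of this stands and it limits the weight of the point. It does not supply the count: listings and flags allow case review, SAE and discontinuation tables capture only what was reported that way, and a maximum is not a number of patients.

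Three stronger readings are tempting, and the documents support none of them.
- A reader might infer that these counts can never be read from a planned table. Steps 2 and 4 of the working show exceptions.
- A reader might infer an error or a broken commitment. Protocol 9.4.2.2 asks only for normal-range shifts and summary statistics.
- A reader might infer that dropping the Hy's law analysis, recorded in the SAP amendment history ("law from Section 4.2.10.2"), was wrong because the tests are still in the panel. That entry describes superseded text, and its stated reason, that data had ceased to be collected, does not say which data. It shows only that a joint table will not appear by default.

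**Conclusion.** The point holds as a limited one. Graded ALT/AST counts and joint ALT/AST–bilirubin counts by arm are not generally recoverable from the planned summary tables. The exceptions are a zero joint count when a margin is zero, and yes-or-no information from by-visit maxima. This is a cheap improvement in safety reporting with low stakes: no endpoint, estimand or commitment is affected, the documents name no hepatic risk, and no event rate is claimed.

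The conclusion rests on the visible text of SAP 3.8.2 and 4.2.10.2, where no redaction falls. Separate regional analysis documents, which SAP 1.1 allows for, were not available.

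**What to change.** Add to SAP 4.2.10.2:

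> For the DB period (by treatment group, safety analysis set) and the OLE period (OLE analysis set), the number and percentage of patients will be presented with maximum post-baseline ALT or AST ≥3×, ≥5× and ≥10×ULN; with maximum post-baseline total bilirubin ≥2×ULN; and with both ALT or AST ≥3×ULN and total bilirubin ≥2×ULN at any time in the period. Denominators are patients with at least one post-baseline value of the test(s) in the period. All data will be used, including repeat and unscheduled tests. Patients meeting the joint criterion will be listed with baseline and all dated ALT, AST, total bilirubin and ALP values.

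The 3×ULN level matches exclusion criterion 24; the other cut-offs are suggestions. A split by baseline category (at or below ULN, above ULN) and a version requiring the bilirubin rise on or after the date of the ALT/AST rise are optional, because cells will be sparse and draws few.

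The cost is SAP wording, one table per period and one listing, some with sparse cells. No protocol change or new data are needed. The fix cannot show transient injury between draws: apart from IPD visits, post-baseline chemistry is scheduled only at Weeks 24 and 56 (DB) and Weeks 80 and 112 (OLE).
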